Negative Pressure Wound
Therapy for Prevention of
Wound Infection after Heart
Surgery

NCT# 02020018

September 23, 2016

IRB Protocol Template

Title: Negative pressure wound therapy for prevention of wound infection after heart surgery

Protocol Version/Date: September 23, 2016

IRB#: 16-007901 (Original 13-001832)

PI: [name] M.D.

Abstract:

Wound-related complications after median sternotomy are important problems associated with increased morbidity and mortality, and lead to increase costs secondary to increase length of hospital stay and the need for repeated surgical procedures in these patients. Risk factors include: chronic obstructive pulmonary disease (COPD), smoking, diabetes, bilateral harvest of the internal thoracic artery, and, in particular, obesity have been identified as major risk factors. Breakdown of skin sutures facilitates entry of bacteria into the deeper layers and presents the initial step in the development of the majority of wound infections after median sternotomy. This theory may explain why the risk of wound infection is particularly high in obese patients, because the shear and traction forces on skin sutures are high. Negative pressure wound therapy have been used in different specialities to treat infected or open wounds, and has been proven to be of great benefit in multiple studies. Its use as a primary prevention has not been the routine after cardiac surgery in high risk patients. We hypothesize that negative pressure wound dressing application on clean skin immediately after suturing in the operating room for 6-7 days will prevent skin breakdown in the early periods after surgery and will decrease the incidence of wound related complications and infection. This may lead to a change in practice when dealing with high risk individuals. The purpose of this study was to compare a new commercially available negative pressure wound therapy (NPWT) system (Prevena Incision Management System; KCI, San Antonio, Tex) and conventional sterile dry wound dressing in a high-risk group (ie, obese patients), with special regard to wound complications and infections. Of note the "Prevena incision management system" is an FDA-approved device with 510K clearance.

Schematic Design of the Study: There will be two groups: the first will include "Prospective non-randomized" part which will include patients who agreed to participate and have wound VAC applied to their incision postoperatively for 6-7 days (this information was collected under IRB 13-001832). The second group will include "retrospective chart review" for standard wound care after heart surgery with no wound VAC.

Aims:

Comparing the outcome of negative pressure wound therapy and conventional sterile dressing for high risk patients undergoing open heart surgery through median sternotomy

Methods

Description of Recruitment Methods:

How will subjects be identified?

Chart review and cardiac surgery database

How will subjects be contacted?

Follow-up routine postoperative visits and chart reviews

Recruitment Materials (if applicable):

Chart review

Subject Population:

Number: 950

The prospective portion will include 300 patients in whom the Prevena wound VAC system will be applied and the retrospective portion will include the remaining 650 patients.

Gender:

Male 450

Female 500
Ages: 18 to 100 years

Inclusion Criteria:

- BMI>30
- Severe COPD
- Steroid-dependent
- Type-I diabetes (insulin-dependent)
- Heart and lung transplant patients
- Preoperative tracheostomy
- Undergoing median sternotomy for open heart surgery between 2013-2014

Exclusion Criteria:

- Thoracotomy
- Type-II diabetes
- BMI<30

Step-by-Step Schedule (include all procedures, therapies – attach a table or flow chart if there are multiple procedures or visits and indicate the window of number of days in which the participant may return for follow-up visits):

N/A

Biospecimen (types, number, volume, processing, storage):

N/A

Plan for Dose Modification if Toxicity occurs (if applicable):

N/A

Statistical Considerations

Endpoints

Primary: wound infection
Secondary: wound breakdown
Length of stay
Re-operation
Mortality due to mediastinitis

Protocol form, page 2

Human Safety Aspects

Risks: Minimal risk study

Individual Subject Stopping Rules (if applicable):

DSMB (if applicable):

Members:

Charter:

Stopping Rules for Efficacy and Safety (if applicable):

Questionnaires that ask about Depression (if applicable)

Included in study? Yes No If "Yes", state the plan of management for subjects with possible depression:

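### Only the VAC group is conditioned on agreement and on a clean incision sutured in the operating room; the shared eligibility list sets no matching condition for the chart controls, which may bias the comparison towards the VAC.

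*Combined protocol and SAP*

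**What the plan says.** The Schematic Design section describes two groups.

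- **VAC group (300).** Labelled "Prospective non-randomized", it consists of "patients who agreed to participate and have wound VAC applied to their incision postoperatively for 6-7 days". The data were gathered under the earlier IRB number. The hypothesis in the Abstract describes the treatment as "negative pressure wound dressing application on clean skin immediately after suturing in the operating room for 6-7 days".
- **Control group (650).** A retrospective chart review "for standard wound care after heart surgery with no wound VAC". The Abstract and Aims name the comparator as a conventional sterile dressing.

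There is one list of inclusion and exclusion criteria, not divided by group. The inclusion criteria are BMI above 30, severe COPD, steroid dependence, type-I diabetes, heart and lung transplant, preoperative tracheostomy, and "Undergoing median sternotomy for open heart surgery between 2013-2014". The exclusions are thoracotomy, type-II diabetes and BMI below 30.

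The primary endpoint is wound infection, and re-operation is a secondary endpoint. The plan gives no expected infection rates, index operation, matching, adjustment or analysis method.

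**The concern.** On paper the two groups meet the same criteria. In practice the VAC group passes through two further filters: the patient agreed, and the incision was in a state to take the device at the end of the operation. A control passes through neither. A high-risk patient whose chest was left open, or who already had a sternal wound infection when the heart operation was done, satisfies the eligibility list and had no VAC.

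This matters because the study asks about prevention. The Abstract's proposed mechanism is that skin sutures give way and let bacteria in. A patient whose skin was not sutured, or whose wound was already infected, cannot inform that question, yet would add to the control infection count. Neither condition is among the risk factors the plan names, so an adjustment built only on those factors would not pick it up.

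The missing index operation adds to the problem. A patient with two sternotomies in the window could enter as a control at the second one, when that operation should count as an outcome of the first.

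**Working it through.** **Entry conditions side by side**

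| Condition | VAC group | Chart controls |
|---|---|---|
| Listed risk factors and exclusions | Yes | Yes (same list) |
| Sternotomy for open heart surgery, 2013-2014 | Yes | Yes (same list) |
| Agreement to participate | Yes (Schematic Design) | Not required |
| Skin sutured in the operating room | Implied by the intervention (Abstract) | Not stated |
| Clean incision | Implied by the intervention (Abstract) | Not stated |
| Defined index operation | Not stated | Not stated |

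**Checking the plan's own figure.** The only figure that can be checked is the total: 300 + 650 = 950, which agrees. With no infection rate, error rate or effect size given, the 950 cannot be derived further.

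**Size of the possible bias.** From the plan: 300 VAC patients and 650 controls. Everything else is assumed:

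- no true device effect;
- infection risk p in the VAC group and in comparable controls;
- a share s of controls who could not have received the device;
- k times the infection risk in that share;
- a two-sided 5% pooled z-test, since the plan names no test.

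Control rate: p_c = p(1 − s + s·k).

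Spurious risk ratio (VAC/control): p/p_c = 1/(1 − s + s·k), which does not depend on p.

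- s = 5%, k = 2: 1/(0.95 + 0.10) = 1/1.05 = 0.952
- s = 10%, k = 3: 1/(0.90 + 0.30) = 1/1.20 = 0.833
- s = 10%, k = 4: 1/(0.90 + 0.40) = 1/1.30 = 0.769
- s = 2%, k = 2 to 4: 1/1.02 to 1/1.06 = 0.980 to 0.943

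The chance of a significant result favouring the VAC was found by summing exact binomial probabilities over every pair of outcomes at 300 and 650, with rates p and p_c:

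| s, k | RR | p = 10% | p = 5% | p = 3% |
|---|---|---|---|---|
| Equal groups | 1.000 | 2.3% | 2.2% | 2.1% |
| 2%, 2 | 0.980 | 2.9% | 2.6% | 2.4% |
| 2%, 4 | 0.943 | 4.3% | 3.4% | 3.0% |
| 5%, 2 | 0.952 | 3.9% | 3.2% | 2.8% |
| 10%, 3 | 0.833 | 13.8% | 8.1% | 5.9% |
| 10%, 4 | 0.769 | 25.5% | 13.4% | 8.9% |

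In patients, a 2% share is 13 of 650, 5% is about 33, and 10% is 65.

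**The case against.** The best case against the point is that the text already narrows the control group more than it may seem.

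- **A reader might infer that a control needs only a sternotomy.** The documents do not say that. The list is not limited to the VAC group, so controls must also meet the risk and exclusion criteria. Sternotomy is only the sole criterion about the operation itself.
- **Operations done solely for sternal infection are already out**, because the sternotomy must be for open heart surgery. What remains is heart operations in patients who already had a sternal infection.
- **A conventional dry dressing suggests a closed incision.** It does, but it describes the comparator. It is not a rule a chart abstractor could apply consistently.
- **The closure and clean-skin wording sits in the hypothesis, not in the criteria, and the timing of agreement is not given.** Both conditions are inferred from a device applied in the operating room. The inference is reasonable, but it remains an inference.
- **A reader might infer that emergencies have no counterpart in the VAC group, so that adjustment could not help.** The plan does not say whether the earlier study enrolled emergencies. If it did, they overlap and adjustment could use them.
- **The direction is not certain.** Very sick patients may die before an infection is recorded, and no follow-up window or rule for deaths is stated. That could lower their recorded rate.

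These points narrow the concern. They do not supply a closure or wound-state condition for controls.

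**Conclusion.** The point holds in limited form. The eligibility list, applied as written, can admit controls whose skin was not closed at the index operation or who already had a sternal wound infection, while the VAC group as described cannot contain them. If they have a higher recorded infection risk, the comparison is biased towards the VAC. The documents do not show that any such patients are among the 650, so this is a gap in the plan and not a demonstrated bias.

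The size rests wholly on assumed shares, risk multiples and infection rates. It could be trivial at a 2% share, or raise the false-positive rate favouring the VAC roughly elevenfold in the worst case shown (25.5/2.3 ≈ 11), which takes the highest value of all three inputs. The point sits within the larger weakness of a non-randomised comparison with no stated analysis, but unlike that weakness it can be removed by a simple filter. It should be changed; confidence in its practical importance is medium.

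**What to change.** Add to the eligibility list, for both arms, judged at the end of the first eligible sternotomy in the 2013-2014 window:

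1. sternotomy skin closed primarily in the operating room;
2. no existing sternal wound infection or mediastinitis at that operation.

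State that this first sternotomy is the index operation, so that later sternotomies count only as outcomes. Compare operative urgency between the arms, and restrict on it only if the earlier study's records show that no emergencies were enrolled; otherwise the restriction would discard patients who do overlap. Report the number excluded by each condition in each arm, and repeat the primary comparison on the unrestricted control set as a sensitivity analysis.

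The cost is a few lines of text and a filter on operative records. There will be somewhat fewer than 650 controls, and the conclusion will apply only to primarily closed incisions, which is the setting the Abstract describes. The filter does not remove selection by agreement itself, which still needs a stated adjustment method.

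### Groups are defined by whether the VAC was applied, so a patient who agreed but was never treated leaves the device group and could be picked up as a control

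*Combined protocol and SAP*

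**What the plan says.** The Schematic Design of the Study describes a prospective, non-randomized device group and a retrospective control group. The device group is "patients who agreed to participate and have wound VAC applied to their incision postoperatively", with data collected under IRB 13-001832. The control group is a chart review "for standard wound care after heart surgery with no wound VAC".

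Subject Population counts the first group as "300 patients in whom the Prevena wound VAC system will be applied" and adds that "the retrospective portion will include the remaining 650 patients".

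Subjects are identified from chart review and the cardiac surgery database. The operation window is 2013-2014. Both are stated once, for the whole study. The three exclusion criteria concern thoracotomy, type-II diabetes and BMI; none concerns earlier consent, withdrawal or a device that was not applied. Statistical Considerations lists endpoints only. It has no analysis set and no rule for patients who agreed but were not treated.

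**The concern.** Agreement comes before the operation. According to the Abstract, the device goes on in the operating room once the skin is sutured. Membership of the device group therefore depends on something settled after enrolment, and events during surgery can influence it. The documents do not say why a planned device might not be applied. Possible reasons include withdrawal, an unstable patient, a chest left open or a surgeon's decision.

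If non-recipients tend to have complicated operations and a higher wound risk, leaving them out lowers the infection rate in the device group. Counting them as controls also raises the control rate. Both shifts favour the VAC on the primary endpoint, wound infection, even if the device does nothing. The allocation is not randomized, so nothing in the design offsets this.

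**Working it through.** **Step 1. Apply the definitions.** Take a patient who agreed under IRB 13-001832, had an eligible sternotomy in 2013-2014 and never received the device.

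- Device group, read as treatment received: not met.
- Control group: met, provided the patient was given standard wound care.
- Exclusion criteria: none removes the patient.
- Source and window: the shared database and the shared 2013-2014 period can both retrieve the patient.
- Device group, read as consent to both participation and application: met. The patient then fits both definitions.

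On either reading the plan needs a rule that it does not contain.

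**Step 2. The plan's own figures.** The totals agree: 300 + 650 = 950. The documents give no infection rate, significance level, power or count of untreated consenters, so the bias cannot be derived from them.

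**Step 3. Illustration on assumed figures.** Assume no device effect, 5% infection in the 300 treated patients, *k* untreated consenters with infection risk *r*, and controls who otherwise share the case mix of all consenters. In the switching case, all *k* are drawn into the 650.

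- Rate in all consenters: M = (300 × 0.05 + k × r) / (300 + k)
- Untreated consenters dropped only: RR = 0.05 / M
- Dropped and counted as controls: C = ((650 − k) × M + k × r) / 650, and RR = 0.05 / C

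| k | r | M | C | RR, dropped only | RR, dropped and switched |
|---|---|---|---|---|---|
| 5 | 15% | 15.75/305 = 5.16% | (645 × 0.05164 + 0.75)/650 = 5.24% | 0.97 | 0.95 |
| 15 | 15% | 17.25/315 = 5.48% | (635 × 0.05476 + 2.25)/650 = 5.70% | 0.91 | 0.88 |
| 30 | 25% | 22.5/330 = 6.82% | (620 × 0.06818 + 7.5)/650 = 7.66% | 0.73 | 0.65 |
| any | 5% | 5.00% | 5.00% | 1.00 | 1.00 |
| 15 | 2.5% | 15.375/315 = 4.88% | (635 × 0.04881 + 0.375)/650 = 4.83% | 1.02 | 1.04 |

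**Step 4. Split the mechanism.** On the log scale, dropping alone accounts for ln 0.913 / ln 0.878 = 70% of the bias in the 15-at-15% case and ln 0.733 / ln 0.653 = 73% in the 30-at-25% case. Switching adds the rest.

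**Step 5. Effect on a false positive result.** Now set 5% as the average risk of all consenters, with 30 untreated among the controls.

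- At twice the average risk: device (330 × 0.05 − 30 × 0.10)/300 = 4.5%, control (620 × 0.05 + 30 × 0.10)/650 = 5.2%, RR 0.86.
- At three times: device (330 × 0.05 − 30 × 0.15)/300 = 4.0%, control (620 × 0.05 + 30 × 0.15)/650 = 5.5%, RR 0.73.

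At an assumed two-sided 0.05 level (normal approximation, pooled variance under the null), the chance of a false result favouring the VAC is 6.4% and 14.6% respectively, against a nominal 2.5%.

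**Step 6. Keep all consenters in the device cohort.** The device rate becomes M and the control rate is M, so RR = 1.00. This follows from the assumption of equal case mix; the design does not guarantee it.

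**The case against.** The strongest objection is that this is silence in the text and not a rule. A reader might infer that the plan moves untreated consenters into the control group. The documents do not support that. The groups are also separated by data source, and someone enrolled prospectively under the earlier IRB does not naturally belong to a retrospective review of the remaining patients. The control definition also requires standard wound care, which a patient with an open chest may not have had. The definition may even be consent-based already, since the phrase can mean agreeing to have the VAC applied, and the count of 300 is in the future tense. This stands as a limit on the claim. It does not close the gap, because the consent reading puts the same patient in both groups.

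A second objection concerns size. The cases favouring the VAC assume non-recipients had three to five times the infection risk of treated patients, and withdrawal gives no evident reason for excess risk. In the 15-at-15% case the gap is 0.7 percentage points, less than half the standard error of the difference: √(0.05 × 0.95/300 + 0.057 × 0.943/650) = 1.55 points. Most of the illustrated bias also comes from dropping these patients, so switching should not be presented as the main driver. All of this stands.

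Third, the handling of withdrawal and non-application may be set out under IRB 13-001832, which is not among the documents. That is possible, but the present plan defines the comparison and should carry the rule itself.

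**Conclusion.** The concern holds in a limited form. The plan groups patients by treatment received, which is settled after enrolment, and nothing keeps an untreated consenter out of the 650 controls. It is not shown that any patient was handled this way, and the number could be zero.

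The direction depends on the risk of the untreated: the bias favours the VAC if their risk was higher than that of other consenters, is nil if equal, and reverses if lower. On the assumed figures with higher risk (5 to 30 untreated, 15% to 25% infection, 5% in the treated), the apparent risk ratio with no true effect runs from 0.95 down to 0.65. A reader might infer that the device result is therefore spurious, or that regrouping makes the comparison unbiased. The documents support neither. The size rests on assumption, and regrouping leaves confounding with never-enrolled controls untouched.

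**What to change.** 1. Remove every patient enrolled under IRB 13-001832 from the control pool before the 650 are drawn.
2. Define the device cohort as all who agreed and had an eligible sternotomy, whether or not the VAC was applied, and follow their outcomes in the chart within the limits of any withdrawal of consent.
3. Report how many were not treated, and why.
4. Present the comparison by VAC applied alongside, as a sensitivity analysis.

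The cost is a few sentences in the plan, a cross-check of the enrolment list against the control extract, and some added chart review for untreated consenters. The list is implied by the prospective collection but not shown, so its existence and completeness should be confirmed first. The effect estimate may be slightly diluted, and the device cohort may exceed 300. If the count of untreated consenters is zero, the check settles the matter.

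### The protocol sets no common infection definition, outcome source or time window for a prospective NPWT group and chart-review controls, so infection rates could differ through ascertainment alone

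*Combined protocol and SAP*

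**What the plan says.** The Schematic Design of the Study section describes two groups whose data arise differently. For the NPWT group, "the first will include 'Prospective non-randomized' part which will include patients who agreed to participate". It then says, of that group's data and of the controls: "this information was collected under IRB 13-001832). The second group will include 'retrospective chart review' for standard wound care". Under Subject Population the NPWT group has 300 patients, and "the retrospective portion will include the remaining 650 patients".

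The endpoint entry under Statistical Considerations reads "Primary: wound infection". It gives no diagnostic criteria, wound depth, assessor or time point. The Step-by-Step Schedule item, which invites a follow-up visit window in days, is answered as not applicable.

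Two other lines mention charts or follow-up, both under Description of Recruitment Methods. Subjects are identified through "Chart review and cardiac surgery database" and contacted through "Follow-up routine postoperative visits and chart reviews". Neither line is split by group, names an outcome or gives a duration. The title block shows that an earlier protocol exists: "IRB#: 16-007901 (Original 13-001832".

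**The concern.** The study's one aim is to compare the two groups, and group may coincide completely with mode of data collection. If it does, and infections are defined, sought or timed differently in the two modes, part or all of an observed difference could be a difference in detection. Neither a larger sample nor adjustment for baseline characteristics can separate that from a device effect.

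The distortion could run either way. Closer observation of study participants would find more infections in the NPWT group and could hide a benefit or suggest harm. A shorter or narrower prospective record would find fewer and could create an apparent benefit. As written, the current protocol neither rules this out nor lets a reader check it.

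**Working it through.** **Reading the text.** For each thing that must be common to both groups:

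| Element | NPWT group | Controls | Common rule stated? |
|---|---|---|---|
| Infection definition | endpoint name only | endpoint name only | No |
| Outcome source | information collected under the earlier IRB number; outcomes not mentioned | chart review | No |
| Time window from surgery | none (schedule not applicable) | none | No |

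The 2013-2014 limit in the inclusion criteria bounds operation dates; it does not set a time from surgery to infection.

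**Stated figures.** 300 + 650 = 950 and 450 + 500 = 950, so the total agrees. No infection rate, effect size, alpha or power is given, so there is no power calculation to reproduce.

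**Illustration.** Only 300 and 650 come from the protocol. Assumed: control infection rate p of 5% or 10%, capture fractions c (the share of true infections recorded), two-sided alpha 0.05 and a pooled z test. Probabilities come from exact enumeration of Binomial(300) and Binomial(650).

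Recorded rates are p × RR × c(NPWT) and p × c(control), so apparent RR = true RR × c(NPWT) / c(control). In each cell the first figure is for p = 5% and the second for p = 10%. The false-finding column assumes no true effect and is in the direction of the distortion.

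| Capture, NPWT / control | Apparent RR if true RR is 1 | False finding | Power if true RR is 0.50 |
|---|---|---|---|
| 100 / 100 | 1.00 | worse 2.8%, 2.7%; better 2.2%, 2.3% | 43%, 77% |
| 95 / 85 | 0.95/0.85 = 1.12 | worse 6.0%, 7.8% | 29%, 56% |
| 95 / 70 | 0.95/0.70 = 1.36 | worse 16.4%, 27.5% | 13%, 25% |
| 85 / 95 | 0.85/0.95 = 0.89 | better 4.5%, 6.6% | 51%, 84% |
| 70 / 95 | 0.70/0.95 = 0.74 | better 12.3%, 23.7% | 66%, 94% |

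The higher power in the last two rows is not a gain, because it comes from exaggerating the effect.

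**Unequal windows.** Assume lognormal time to onset (log-SD 0.7), 30 days of observation in one group and 90 in the other, and no true effect. With the shorter window in the NPWT group, the apparent RR is F(30)/F(90), where F is the cumulative onset distribution:

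- median onset 7 days: 0.981/1.000 = 0.98; false benefit 2.5%, 2.8%
- median onset 21 days: 0.695/0.981 = 0.71; false benefit 15.0%, 29.6%

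With the windows reversed at a median of 21 days, the false finding is harm, in about 20% and 34%.

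**Differences in definition.** A looser definition in one group adds false positives, which a capture ratio does not describe. Take p = 5%, true RR 0.50, perfect classification in controls and full capture in the NPWT group:

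- NPWT specificity 99%: (0.025 + 0.975 × 0.01)/0.05 = 0.03475/0.05 = 0.70, a factor of 1.39 on the true RR
- NPWT specificity 98%: (0.025 + 0.975 × 0.02)/0.05 = 0.0445/0.05 = 0.89, a factor of 1.78

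**The case against.** The strongest reply is that the statement about earlier collection directly follows the agreement to participate and the application of the device, and does not mention outcomes. It may cover only enrolment and device use. Outcomes in both groups could then come from charts, and the unsplit recruitment lines are compatible with that. The earlier protocol may also contain a definition and a follow-up window. And not applicable is a reasonable answer to a question about visits if no new visits are planned.

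Most of this stands. A reader might infer that infections really were ascertained differently in the two groups, or that the comparison is already biased in favour of the device. The documents support neither inference: they show no actual difference in ascertainment and give no direction.

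The reply does not supply the missing rule. The recruitment lines answer how subjects are identified and contacted, not how outcomes are determined. Even a shared chart source would leave the definition and window open. The current protocol ties the earlier IRB number to the NPWT information only; it neither restates a definition from there nor applies one to controls.

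It is also fair to object that the magnitudes rest wholly on assumptions, and that with early onset the 30- against 90-day difference has almost no effect. That limits how serious the point can be said to be.

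**Conclusion.** The point holds as a gap in the current protocol that should be closed, at low cost. No common infection definition, outcome source or window is set for two groups whose data collection may differ entirely, so infection rates could differ through ascertainment alone.

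Its size cannot be established. Under the assumptions shown, a false directional finding ranges from about the nominal 2.5% to roughly a third of studies, and a true effect may be masked or exaggerated. If definition, source and window prove to be the same in both groups, there is no bias from those differences.

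A stronger reading, that the prospective and retrospective design is itself unusable for this endpoint, does not follow: the fix keeps the design. Equal ascertainment would not remove confounding from the non-randomized comparison, which is a separate matter.

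**What to change.** Before outcomes are compared, add two short paragraphs to the protocol:

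1. **Definition and window.** Give one written definition of wound infection and one fixed window from the date of surgery. If the earlier protocol has them, restate them and apply them unchanged to the controls.
2. **Source.** Ascertain wound infection in both groups from the medical record with the same abstraction form, and record the date of last charted contact in both.

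Re-abstract the NPWT records, up to 300, only if their outcomes did not already come from charts under that definition and window. Report infections known only from prospective study data separately, and include them in a sensitivity analysis.

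Any misclassification sensitivity analysis should run in both directions and vary specificity as well as capture. A capture ratio alone is not enough. For example, hypothetical counts of 15/300 and 65/650 give RR 0.50 (SE of log RR = √(1/15 − 1/300 + 1/65 − 1/650) = 0.278; 95% CI 0.29 to 0.86). Dividing by an NPWT-to-control capture ratio of 0.86 brings the upper limit to 1, but that tipping point says nothing about false positives.

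**Cost.** Review of the 650 control charts is already planned. The addition is at most 300 further abstractions, assuming the team can access those records. A few NPWT infections known only from study data may leave the primary count. A shared source also cannot equalise the charts themselves if study contact affected what was charted; the report should say so.

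### Could the control definition, no wound VAC, remove infected controls who were later treated with a VAC?

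*Combined protocol and SAP*

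**What the plan says.** The Schematic Design of the Study sets out two groups. The prospective patients agreed to take part and "have wound VAC applied to their incision postoperatively for 6-7 days"; their data were collected under IRB 13-001832. The retrospective patients are reviewed "for standard wound care after heart surgery with no wound VAC".

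Subject Population describes the device group again, as "300 patients in whom the Prevena wound VAC system will be applied", and gives the remaining 650 of the 950 to the retrospective portion. The Abstract and the Aims both name a conventional sterile dressing as the comparator.

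The Abstract mentions two uses of negative pressure therapy. It says such devices "have been used in different specialities to treat infected or open wounds", and of the preventive use: "Its use as a primary prevention has not been the routine after cardiac surgery". Its hypothesis concerns "application on clean skin immediately after suturing in the operating room for 6-7 days".

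Subjects are identified through "Chart review and cardiac surgery database", and the Inclusion Criteria require "Undergoing median sternotomy for open heart surgery between 2013-2014". The Exclusion Criteria list thoracotomy, type-II diabetes and BMI below 30. Neither list mentions VAC use or wear time. No analysis set is defined. The primary endpoint is wound infection, with no time window.

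**The concern.** The control description carries no time point and no purpose. A VAC can be the preventive dressing under study, or it can be a treatment for the very outcome being counted. If the phrase is taken to mean no VAC at any time, a control who became infected and was then treated with one fails the definition. A device patient with the same course still meets the device-group definition. Membership of one group alone would then depend on the outcome.

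The timing makes this possible in practice. The operations precede the protocol date by about two to three years, so infection and any later VAC may already be in the chart when it is accepted or rejected.

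A weaker form arises in the device group. If 6-7 days were a membership rule, patients whose device came off early because of a wound problem would drop out, and that would favour the device. The two errors run in opposite directions, so the net direction would be unknown. Wound breakdown, length of stay, re-operation and mortality due to mediastinitis could be affected in the same way.

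**Working it through.** **The plan's own figures.** 300 + 650 = 950 and 450 + 500 = 950, so the total is consistent. No alpha, power, infection rate or effect size is given, so there is no sample-size calculation to reproduce and none that this point could upset.

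**How large the bias could be under the literal reading.** Let p be the true infection risk in a group and q the share of infected patients dropped, with no uninfected patients dropped. The observed risk is

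r(p, q) = p(1 − q) / (1 − pq),

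and the apparent risk ratio (RR) is r(p × true RR, q device) / r(p, q control). Every p and q below is an assumption.

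At p = 0.08 and q = 0.25, r = 0.08 × 0.75 / (1 − 0.02) = 0.0612. Patients lost: 650 × 0.08 × 0.25 = 13 controls, or 300 × 0.08 × 0.25 = 6 device patients.

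| True RR | q control | q device | Apparent RR, p = 8% | Range, p = 5-10% |
|---|---|---|---|---|
| 1.00 | 0.25 | 0 | 0.0800/0.0612 = 1.31 | 1.30-1.32 |
| 1.00 | 0 | 0.25 | 0.0612/0.0800 = 0.77 | 0.76-0.77 |
| 1.00 | 0.25 | 0.25 | 1.00 | 1.00 |
| 1.00 | 0.25 | 0.10 | 1.19 | 1.18-1.19 |
| 1.00 | 0.10 | 0.25 | 0.84 | 0.84-0.85 |
| 0.60 | 0.25 | 0 | 0.0480/0.0612 = 0.78 | 0.78-0.79 |
| 0.60 | 0.50 | 0 | 0.0480/0.0417 = 1.15 | 1.14-1.17 |

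With a true RR of 0.50 and control risks from 3% to 15%, dropping half of the infected controls gives an apparent RR of 0.93-0.98, so a real halving of risk would nearly vanish.

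These figures are the extreme for each share lost, because a real rule would also remove some uninfected patients. For example, drop 25% of infected and 10% of uninfected device patients at p = 0.08 with no true effect. The observed risk is 0.06 / (0.06 + 0.92 × 0.90) = 0.06 / 0.888 = 0.0676, and the RR is 0.0676/0.0800 = 0.84 rather than 0.77.

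**Whether the text supports that reading.**

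1. The control phrase directly follows the device-group phrase "have wound VAC applied to their incision postoperatively for 6-7 days". The plain sense is the same device, absent.
2. Subject Population uses the term wound VAC for the Prevena system itself.
3. The Abstract and the Aims name the comparator as a conventional sterile dressing, which is a choice made at closure.
4. The title and the hypothesis concern prevention on clean, closed skin.
5. No exclusion criterion mentions a later VAC.

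Under this reading q control = 0, all 650 controls remain, and the apparent RR equals the true RR as far as this source of bias goes.

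**Device group.** The Abstract gives 6-7 days as part of the hypothesised regimen, and "300 patients in whom the Prevena wound VAC system will be applied" sets no wear condition. The ordinary reading keeps every patient in whom the device was applied, so q device = 0. How short wear was handled under IRB 13-001832 is not in these documents.

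**The case for a change.** The best case for a change is that a chart abstractor works from the words on the page, and those words contain no instruction to ignore a later VAC. The outcome may already be visible when the chart is judged, the literal reading affects the two groups unequally, and two sentences tying each group to the dressing placed at closure would settle it without touching treatment. The arithmetic shows that the bias need not be small if the share lost is large.

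Some of this stands. The rule is not written down, controls are selected after the fact, and the arithmetic is right for the assumptions used. But the objection needs the less natural reading. It also needs infected sternotomy controls at this site to have been treated with a VAC in appreciable numbers. The Abstract speaks only of use in different specialities, which does not establish that. The device-side argument rests on handling under a protocol that is not available here. Nothing in the plan orders either exclusion.

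**Conclusion.** The concern does not call for a change. The control wording is incomplete if taken alone, but the neighbouring device-group sentence, Subject Population, the Abstract and the Aims fix its ordinary meaning: no preventive device on the closed incision. Read that way, a control who becomes infected and later receives a VAC stays in the control group, and this source of bias is zero. The 6-7 days is the planned regimen, and no device-side bias is shown.

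The illustrative risk ratios, from 0.77 to 1.31 under no true effect at 8% infection, describe what a literal and unlikely reading could do. They rest wholly on assumed infection risks and shares lost, and on dropping no uninfected patients. This is a gap in detail that analysts of a prevention study would fill sensibly. The conclusion would need another look only if there were evidence that controls were in fact rejected for a later therapeutic VAC, or device patients for short wear. The documents contain none.
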